#### **9.2.11 Time to Response in VRS**

The time to response in VRS (time to the first response in VRS in each subject) will be analyzed in the same manner as the time to response in IGA. Subjects with a VRS score of 0 (none) or 1 (mild) with an improvement by at least 1 grade from the baseline are defined as responders. The starting point is baseline. Subjects who have failed to achieve a response will be treated as censored on the day of the final VRS assessment.

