3.3.3 Pharmacokinetics

Plasma trough concentration of OPA-15406 (trough concentration at Week 1, Week 4, and Week 8)

- 1) Plasma trough concentrations of OPA-15406 (prior to IMP administration at Week 1, Week 4, and Week 8 of IMP administration; all subjects)
- 2) Plasma concentration of OPA-15406 (prior to IMP administration and 2 hours, 4 hours, and 8 hours postdose on Day 1 and at Week 4; specific sites [target of 6 subjects from each group])
 - Pharmacokinetic parameters of OPA-15406: C_{max} , t_{max} , AUC_{0-8h} on Day 1 and at Week 4 of IMP administration
 - Accumulation of OPA-15406: Ratio of C_{max} and AUC_{0-8h} at Week 4 and on Day 1 of IMP administration

[Rationale for variable selection]

[Efficacy]

The primary variable of IGA is an indicator to assess the severity of AD and also a reliable indicator to determine the efficacy of the IMP; therefore, IGA has been established as the primary efficacy endpoint. IGA is evaluated based on the severity of overall symptoms (erythema, infiltration, papules, effusion, and scab formation) at treatment area and does not include other factors (eg, excoriation, symptoms of lichenification, severity of each part, subjective symptoms, affected BSA). Therefore, EASI, VAS and VRS for pruritus, DLQI, POEM, and affected BSA have been established as the secondary variables to evaluate the efficacy from multiple

points of view.
[Safety]
To appropriately assess the safety of this product.
[Pharmacokinetics]
To determine pharmacokinetics of OPA-15406 and the internal exposure to OPA-15406 in Japanese AD patients.

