5.2 Inclusion Criteria

Subjects who meet all of the following criteria will be eligible for inclusion in this trial.

At the screening examination:

- 1) Sex: Either male or female
- 2) Hospitalization status: Outpatient
- 3) Age: 15 to 70 years, inclusive (at time of obtaining informed consent)
- 4) Able to provide written informed consent. For subjects under 20 years of age, written informed consent must be obtained from both the subject and the subject's legal guardian.
- 5) Diagnosis of AD based on the criteria of Hanifin and Rajka¹
(Appendix 1)
- 6) History of AD for at least 3 years

At screening and baseline examinations:

- 7) AD affecting $\geq 5\%$ to $\leq 40\%$ of BSA
- 8) IGA score of 2 (mild) or 3 (moderate)

[Rationale for Inclusion Criteria]

- 1) AD occurs in both males and females.
- 2) Most patients to be included in this trial are outpatients.
- 3) In the phase 1 trial in healthy Japanese adult subjects (271-14-001) and the phase 2 trial in patients aged 10 years and older outside Japan (271-12-205), no particular safety concerns were identified. Therefore, in the present trial, adult patients (aged 15 years and older) will be included.
- 4) To conduct the trial without any ethical problems.
- 5) The criteria of Hanifin and Rajka have been most commonly used worldwide and have the same major diagnostic criteria as those of the Japanese Dermatological Association; therefore, the criteria can be used also in Japan without problems.
- 6) -8) To appropriately evaluate the efficacy of the IMP on the target disease.

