Appendix 1 Diagnostic Criteria for Atopic Dermatitis (Hanifin & Rajka)

A. Must have 3 or more basic features described below
 
 1) Pruritus 2) Typical morphology and distribution 
 Flexural lichenification in adults Facial and extensor involvement in infants and children 3) Chronic or chronically-relapsing dermatitis 4) Personal or family history of atopy (asthma, allergic rhinitis, atopic dermatitis)

B. Must have 3 or more following minor features:
 
 1) Xerosis 2) Ichthyosis, palmar hyperlinearity, keratosis pilaris 3) Immediate (type 1) skin test reaction 4) Elevated serum IgE 5) Early age of onset 6) Tendency toward cutaneous infections (especially Staph. aureus and Herpes simplex)/impaired cell-mediated immunity 7) Tendency toward non-specific hand or foot dermatitis 8) Nipple eczema 9) Cheilitis 10) Recurrent conjunctivitis 11) Dennie-Morgan infraorbital fold 12) Keratoconus 13) Anterior subcapsular cataracts 14) Orbital darkening 15) Facial pallor, facial erythema 16) Pityriasis alba 17) Anterior neck folds 18) Itch when sweating 19) Intolerance to wool and lipid solvents 20) Perifollicular accentuation 21) Food intolerance 22) Course influenced by environmental and emotional factors 23) White dermographism, delayed blanch

Date _____ (examination)

Subject Number _____ -S-

**Appendix 2 Visual Analogue Scale (VAS) Sheet for
Pruritus**

No Itching

Maximum Itching

0 _____ 100

Date _____ (examination)

Subject Number ___-S-

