## 5 Statistical Analysis Sets

### 5.1 Definitions of Analysis Sets

#### 5.1.1 Full Analysis Set

The full analysis set (FAS) consists of all subjects who have received the IMP at least once.

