## **9 Efficacy Analyses**

Efficacy analyses will be conducted in the FAS.

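### Time to VRS response keeps subjects with no itch at baseline in the risk set, although they can never meet the response definition

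*SAP*

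**What the plan says.** SAP 9.2.11 counts as a responder any subject with a "VRS score of 0 (none) or 1 (mild) with an improvement by at least 1 grade from the baseline". Protocol 11.3.1.2 has the same definition. Protocol 7.2.1.4 gives the scale as 0 (none) to 3 (severe).

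For everyone else, SAP 9.2.11 states: "Subjects who have failed to achieve a response will be treated as censored on the day of the final VRS assessment". The method is taken over from time to IGA response (SAP 9.2.10): Kaplan-Meier curves, numbers at risk, a log-rank test of each active arm against vehicle, and the median time.

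SAP Section 9 states: "Efficacy analyses will be conducted in the FAS". SAP 5.1.1 adds: "The full analysis set (FAS) consists of all subjects who have received the IMP at least once". Neither document limits the VRS analysis by baseline VRS or says how a baseline score of 0 is handled.

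The inclusion criteria (protocol 5.2) set no minimum itch score. The rationale for variable selection in protocol Section 3.3 says that IGA "does not include other factors (eg, excoriation, symptoms of lichenification, severity of each part, subjective symptoms, affected BSA". Pruritus enters only through the Hanifin-Rajka diagnosis, where it is one of four basic features and Appendix 1 asks for three: "Must have 3 or more basic features described below".

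**The concern.** Time to response should describe how quickly itch improves. A subject without itch at the baseline reading has nothing to improve on this scale and is not at risk of the event, but the plan counts that subject in every risk set up to the last VRS reading. The reported response rates would then mix speed of relief with the share of subjects who had no itch to begin with.

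The IGA analysis that serves as the model does not have this problem. Entry requires a baseline IGA of 2 or 3, so every eligible subject can reach 0 or 1 with a 2-grade fall. VRS has no such entry guarantee.

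A baseline score of 0 is possible in practice. Mild disease is eligible. Protocol 7.2.1.4 gives VRS no recall period, whereas the VAS covers the last 24 hours. Low- or medium-potency topical corticosteroids may in some cases be used until the baseline examination (protocol 5.3 and 6.3.1).

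**Working it through.** **The plan's own figure.** The documents give no design figure for time to VRS response. The only one, 54 per group, is for the primary IGA endpoint. It reproduces with Fisher's exact test at 20.93% v 2.70% (power 79.1% at 53 per group, 80.2% at 54) and does not bear on this point.

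**Who can respond.** Response needs a final score of 0 or 1 and a fall of at least 1.
- Baseline 3 or 2: reaching 1 or 0 qualifies.
- Baseline 1: reaching 0 qualifies.
- Baseline 0: would need -1, which is impossible.

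Only baseline 0 is affected.

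**Effect on the curves.** Let p be the share with baseline VRS 0 and r the response rate by Day 7 among the rest. The displayed rate is r × (1 - p), with a ceiling of 1 - p. The median is reached only if r is at least 0.5/(1 - p). Both p and r are assumptions; take r = 60% on active and 40% on vehicle.

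| p | ceiling | 60% shown as | 40% shown as | r needed for a median |
|---|---|---|---|---|
| 0% | 100% | 60% | 40% | 50% |
| 5% | 95% | 57% | 38% | 53% |
| 10% | 90% | 54% | 36% | 56% |
| 15% | 85% | 51% | 34% | 59% |

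**Effect on the log-rank test.** Simulation with 60 per arm (the planned size), 3,000 trials per setting, exponential response times observed at 16 readings (the number of timepoints in SAP Table 6.4-2), two-sided 5%. Two assumed scenarios:
- 60% v 40% responding by Day 7.
- Hazards of 0.16 and 0.095 per reading, so 1 - exp(-16 × 0.16) = 92% and 1 - exp(-16 × 0.095) = 78%.

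Power with all FAS, then with baseline VRS of 1 or more:

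| p | 60% v 40% | loss | 92% v 78% | loss |
|---|---|---|---|---|
| 0% | 62%, 62% | 0 | identical | 0 |
| 5% | 58%, 60% | 2 | 66%, 75% | 9 |
| 10% | 54%, 58% | 4 | 54%, 71% | 17 |
| 15% | 49%, 55% | 6 | 46%, 69% | 23 |

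The 60% v 40% figures at 15% use exactly 9 VRS 0 subjects per arm. A repeat of the 92% v 78% runs gave losses of 8, 16 and 25 points. In the 60% v 40% scenario the log-rank estimate of the hazard ratio falls from 1.83 to 1.79, 1.77 and 1.75 at p = 5%, 10% and 15%.

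**Why the scenarios differ.** Take p = 10%, so 6 VRS 0 and 54 itchy subjects per arm.
- At 92% v 78%, about 54 × 0.077 = 4.2 itchy active and 54 × 0.219 = 11.8 itchy vehicle subjects remain at Day 7. The true hazard ratio is 0.16/0.095 = 1.68. The apparent one at that time is 1.68 × (4.2/10.2)/(11.8/17.8), about 1.04.
- At 60% v 40%, 21.6 and 32.4 remain. The true ratio is ln 0.4/ln 0.6 = 1.79 and the apparent one is 1.79 × (21.6/27.6)/(32.4/38.4), about 1.66.

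The damage grows as itchy subjects leave the risk set and the VRS 0 subjects come to dominate it.

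**No true effect (40% v 40%).** Rejection with all FAS is 5.2%, 4.9% and 5.0% at p = 5%, 10% and 20%.

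**Chance imbalance.** Allocation balances only site and baseline IGA. With 60% v 40%, 12 VRS 0 subjects on active and 6 on vehicle give a hazard ratio of 1.48 (1.83 when they are excluded); 6 and 12 give 2.05 (1.82 when excluded).

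**The case against.** **Entry criteria.** A reader might infer that only IGA and BSA govern entry, so that many subjects will have no itch. The documents do not support that. Protocol 5.2 also requires a Hanifin-Rajka diagnosis and at least 3 years of disease. Protocol 5.3 excludes patients who are satisfied with their current treatment and those who cannot stop systemic or topical antihistamines from 7 days before baseline. Together these make VRS 0 less likely. They do not rule it out, so the gap stands, but p may be close to zero.

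**Size.** Quoting only the 92% v 78% scenario would suggest a large loss of power. Nothing in the documents supports those rates over 60% v 40%, where the loss is about a quarter as large. Only the range can be defended.

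**False positives.** A reader might infer from the imbalance example that the test is invalid. It is not: imbalance in a baseline factor is ordinary randomisation noise, and type I error stays near 5%. What remains is that an observed imbalance can move the estimate either way.

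**Choice of question.** The all-FAS curve does estimate something: the share of all treated subjects who attain an itch response. That is a reason to keep it as supportive. It is a poor main answer to how fast itch improves.

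**Importance.** Under SAP 6.6.1, p-values outside the primary variable are for reference only. VRS change from baseline is analysed separately with baseline as a covariate (SAP 9.2.5, by reference to 9.2.3). This limits the consequence and does not remove the flaw.

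**Conclusion.** The point holds as a modest defect in a secondary analysis. As written, any subject with baseline VRS 0 is counted as at risk of an event that the definition makes impossible. Balanced numbers of such subjects lower all three curves, lengthen or remove medians, and attenuate both comparisons with vehicle when the drug works.

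The size depends on two quantities the documents do not give: the share at VRS 0 and the VRS response rates. Over assumed shares of 0% to 15%, the power loss runs from 0 to about 6 points at 60% v 40% and from 0 to about 23 points at 92% v 78%. If no subject scores 0, nothing changes. The primary IGA analysis, the sample size and time to IGA response are unaffected.

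**What to change.** Before unblinding, change SAP 9.2.11 so that the Kaplan-Meier curves, numbers at risk, log-rank tests and medians for time to VRS response are run in FAS subjects with baseline VRS of 1 or more. Report the number with baseline VRS 0 by arm. Keep the all-FAS version as a supportive analysis, and keep all FAS subjects in the VRS change-from-baseline analysis. Since protocol 11.3.1.2 carries no such restriction, record the change and its reason in SAP 13.1, as protocol 11.4 requires.

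The cost is a line or two of text and one filter on a value already collected. The filter uses a pre-treatment value, so the comparison between randomised arms is preserved. In both scenarios power rises despite fewer subjects. The drawbacks are a slightly smaller denominator and a result that applies only to subjects with itch at baseline. Timing matters: under protocol 11.4, a change made after unblinding must be reported apart from the planned analyses.

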### **9.3 Other Efficacy Endpoints**

Not applicable.

### **9.4 Adjustments for Covariates**

In the analysis of the incidence of success in IGA, the primary analysis, the Cochran-Mantel-Haenszel test stratified by baseline IGA (mild or moderate) will be conducted.

## **9.5 Subgroup Analysis**

Incidence of success in IGA will also be analyzed in the following subgroups in the same manner as described in [Section 9.1](#).

Age: <18 or  $\geq 18$  years old

Gender: Male or female

Baseline IGA score: 2 (mild) or 3 (moderate)

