6.4 Method of Minimizing or Avoiding Bias

This trial is a randomized, double-blind trial.

The IMP allocation manager will prepare a master “random allocation table” (hereinafter, “randomization table”) and conduct IMP coding according to the operating procedures for randomization. Also, the IMP allocation manager will prepare an emergency code list for use in emergencies such as the occurrence of a serious adverse event.

The investigator, subinvestigator, and subjects are blind to the IMP randomization code. Except for some designated personnel, the sponsor’s trial staff, including the personnel of contract research organizations, are also unable to access the IMP randomization code during the trial period.

Prior to the trial start and unblinding, the IMP allocation manager will confirm that the IMPs are indistinguishable. The randomization table is sealed by the IMP allocation manager just after completion of IMP randomization and it is kept under strict control until unblinding after fixation of all CRFs and the database.

The emergency code list will be kept under strict control by the registration system until the end of the trial. If a medical emergency occurs in a subject and knowledge of his or her IMP randomization code is considered important for treatment, the emergency code will be broken according to the “[8.2.4 Emergency Code Breaking \(Procedure for Unblinding During the Trial Period\)](#).”

When IMPs are recovered by the sponsor prior to unblinding, they are to be recovered sealed by the IMP allocation manager.

The subjects will be allocated to the 0.3% OPA-15406 group, the 1% OPA-15406 group, and the vehicle group in a ratio of 1:1:1 using dynamic allocation to ensure

balance within the trial sites and that of the baseline IGA (mild or moderate at the baseline examination).

The results of drug concentration measurements will not be revealed until unblinding at the end of the trial.

7 Observations/Examinations/Variables, Methods and Implementation Timings

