11.3.5 Subgroup Analysis

For the incidence of success in IGA at Week 1, Week 4, and Week 8, the analysis will be performed in the same manner as that for the primary variable by subgroups of baseline IGA (mild or moderate). Also, the frequency distribution will be generated by the trial sites.

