### 12.2 Rationale for the Number of Subjects

In the phase 2 trial outside Japan (271-12-205), the primary variable of incidence of success in IGA was 20.93% in the 1% OPA-15406 group and 2.70% in the vehicle group, respectively. In the present trial, with the assumption that the difference in incidence of success in IGA between the 1% OPA-15406 group and the vehicle group is similar to that obtained in the foreign trial, a sample size of 54 subjects per group at a two-tailed 5% level of significance was calculated with at least an 80% power. In consideration of possible discontinuations and dropouts, the number of subjects is established as 60 subjects per group.

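### The subgroup plan repeats the within-subgroup test and never estimates the difference in effect between subgroups, so its p-values cannot show whether the effect differs

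*SAP*

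**What the plan says.** SAP 9.5 names three factors: age (under 18, or 18 and over), gender, and baseline IGA (mild or moderate). Its whole instruction on method is: "Incidence of success in IGA will also be analyzed in the following subgroups in the same manner as described in" Section 9.1. Protocol 11.3.5, for Weeks 1, 4 and 8, says that "the analysis will be performed in the same manner as that for the primary variable by subgroups of baseline IGA (mild or moderate").

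SAP 9.1 contains:

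- a Cochran-Mantel-Haenszel (CMH) test of each dose against vehicle, stratified by baseline IGA;
- the sequence that tests 1% first and 0.3% only if 1% succeeds at two-sided 0.05;
- the Mantel-Haenszel risk difference with a 95% confidence interval;
- a Clopper-Pearson interval for each arm.

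Neither document plans an interaction test, a homogeneity test or an estimate of the difference between subgroup effects. The exploratory logistic regression in Protocol 11.3.1.1 had treatment and baseline IGA as explanatory variables and no interaction term, and SAP 13.1 drops it.

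**The concern.** A subgroup analysis asks whether the treatment effect differs between groups. A p-value computed inside one subgroup asks only whether there is an effect in that subgroup. One significant and one non-significant result do not amount to a comparison, because each depends on the size of its subgroup as well as on the effect.

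Baseline IGA is where this matters most. Success requires a score of 0 or 1 and an improvement of at least two grades (Protocol 3.3.1.1). A subject who starts at 2 must therefore reach 0, while one who starts at 3 can succeed at 0 or 1. The effect on this endpoint could truly differ by stratum, and two separate p-values cannot tell a true difference from chance. What is at stake is the reading of a supportive table, not the primary result.

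**Working it through.** **Inputs from the documents**

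- Planning rates: "incidence of success in IGA was 20.93% in the 1% OPA-15406 group and 2.70% in the vehicle group" (SAP 12.2), a difference of 20.93 − 2.70 = 18.23 points.
- Size: "a sample size of 54 subjects per group at a two-tailed 5% level of significance was calculated with at least an 80% power", after which "the number of subjects is established as 60 subjects per group" (SAP 12.2).
- Allocation: "in a ratio of 1:1:1 using dynamic allocation", with baseline IGA as a balancing factor (Protocol 6.4). Equal arm sizes within each IGA stratum are therefore a fair approximation.

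**Assumptions not in the documents**

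- The whole-trial rates apply equally in both strata.
- The mild/moderate split is unknown, so a range is shown.

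**The plan's own figure.** The exact power of Fisher's test at these rates is 79.1% with 53 per group and 80.2% with 54, so 54 is reproduced. The exact power of the CMH test is 89.2% at 54 and 92.3% at 60.

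**Power within one stratum.** Take n per arm, x responders on active and y on vehicle, and m = x + y. The statistic is Q = (x − m/2)² / V, with V = n²·m·(2n − m) / [(2n)²·(2n − 1)]. A stratum is significant if Q > 3.8415 in favour of active. Power is the sum of the binomial probabilities over such (x, y).

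**Split verdict.** With powers pA and pB in the two strata, P(exactly one significant) = pA(1 − pB) + pB(1 − pA).

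| Split per arm | Power, smaller stratum | Power, larger stratum | Exactly one significant |
|---|---|---|---|
| 30/30 | 66.8% | 66.8% | 44.3% |
| 24/36 | 54.7% | 75.7% | 47.6% |
| 20/40 | 44.0% | 80.2% | 53.6% |
| 18/42 | 37.8% | 82.1% | 57.8% |
| 15/45 | 27.7% | 82.1% | 64.3% |
| 12/48 | 17.2% | 84.7% | 72.7% |
| 6/54 | 1.7% | 89.2% | 87.8% |

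Two rows in full:

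- 30/30: 2 × 0.668 × 0.332 = 0.443.
- 20/40: 0.440 × 0.198 + 0.802 × 0.560 = 0.536.

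At 30/30, both strata are significant in 44.7% of trials and neither in 11.0%. Two variations give similar results:

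- The normal approximation at 30/30 gives 59.4% power per stratum and a split in 48.2%.
- For the 0.3% dose taken alone, the foreign phase 2 rates (14.63% against 2.70%, Protocol 1.2.2.4) give a split in 47.9% at 30/30.

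**The direct contrast.** The standard error of one stratum's risk difference at n = 30 is √[(0.2093 × 0.7907 + 0.0270 × 0.9730)/30] = 0.0800. The difference between two such strata has standard error 0.0800 × √2 = 0.113, so the 95% half-width is 1.96 × 0.113 = 0.222, about 22 points. In simulation (400,000 runs, identical effects, 30/30), a Wald test of this contrast signalled a difference in 4.4% of trials. If one stratum had the full 18.23 points and the other none, its power would be only 46% (simulated) to 52% (normal approximation).

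**Zero cells.** A vehicle stratum of 30 has no responders with probability 0.973³⁰ = 0.44. A simple Wald variance for that arm is then zero.

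**The case against.** The strongest reply is that the plan gives more than p-values. Repeating SAP 9.1 carries the risk difference and its 95% interval into every subgroup, so effect sizes will stand side by side. This holds. A reader might infer that p-values are all that is left to compare, and the documents do not support that. What is missing is an interval for the difference between the two effects.

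Second, Protocol 11.3.7 and SAP 6.6.1 tie the closed procedure to the primary analysis and treat p-values for variables other than the primary one as reference only, without adjustment. Those sentences do not literally name subgroups of the primary endpoint, but nothing in either document rests a claim on a subgroup result. This limits the weight of the point.

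Third, a reader might infer that the mild/moderate result will decide the population of the next trial. Neither document says so; the stated objectives and subgroup sections attach no decision to it.

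Fourth, a reader might take a split verdict as bound to occur about half the time, or as mainly an artefact of power. Both go too far. The figures depend on an assumed split and on equal rates in both strata, and the stricter requirement for mild subjects makes equal rates uncertain.

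Finally, the direct contrast is weak and could itself be misread, with a non-significant interaction taken as equal effects. That is a sound warning about how the contrast is reported. It is not a reason to leave the contrast out.

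**Conclusion.** The gap is real and small. Both documents repeat the within-subgroup analysis and neither plans a between-subgroup contrast, so the subgroup p-values cannot answer whether the effect differs.

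If the planning rates apply equally in both IGA strata, split verdicts range from 44% of trials with equal strata to 88% at 6/54 per arm, against about 4% false signals from a direct contrast at 30/30. The split and the equal rates are assumptions. No figure is claimed for gender or age, whose subgroup sizes are also not given. The primary conclusion is unaffected; this is a worthwhile improvement to a supportive analysis.

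**What to change.** In SAP 9.5:

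1. Keep the subgroup success rates and the risk differences with 95% confidence intervals.
2. Drop the within-subgroup p-values and the 1%-then-0.3% sequence.
3. For each dose and each factor, add the difference between the two subgroup risk differences. Give it a 95% interval from a method valid with zero cells, for example a MOVER interval built from score limits, and one descriptive interaction p-value. With three factors and two doses, that is six contrasts at Week 4, unadjusted and labelled as such.
4. State that the contrast is imprecise (about ±22 points at 30/30) and that a non-significant interaction is not evidence of equal effects.
5. State that for a very small subgroup only rates and intervals are shown. Age under 18 may be one, since eligibility starts at 15 and it covers only ages 15 to 17.
6. Note that inside a baseline IGA subgroup the stratification in Section 9.1 has a single level.

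The cost is SAP wording and one extra line per subgroup table, using data already collected. The downside is wide intervals, which should be shown as they are.
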